## 6.5 Windowing Conventions

Not Applicable

## 6.6 Statistical Tests

The default significant level will be (5%) confidence intervals will be 95% and all tests will be two-sided, unless otherwise specified in the description of the analyses.

## 6.7 Common Calculations

For quantitative measurements, change from baseline at visit X will be calculated as:

- Test Value at Visit X – Baseline Value

For quantitative measurements, percentage change from baseline at visit X will be calculated as

- $((\text{Value at post-baseline visit X} - \text{Baseline value}) / \text{Baseline value}) * 100$

## 6.8 Software Version

All statistical analyses including PK and ADA, summaries and listings will be generated using SAS Version 9.4 or higher (SAS Institute, Inc., Cary, North Carolina). Graphics may be prepared using the same version of SAS.

# 7 STATISTICAL CONSIDERATIONS

## 7.1 Adjustments for Covariates and Factors to be Included in Analyses

Not Applicable

---

Document: \\eedc-vnasc01\Biosdata\Biosidus\Agalsidase Beta\YZAA1358\Biostatistics\Documentation\SAP

Author: [name]

Version Number: V1.0

Version Date: 08May2025

Template No.: CS\_TP\_BS016 Revision 7

Reference: CS\_WI\_BS005

Effective Date: 01Nov2021

Copyright © 2009, 2010, 2012, 2016, 2018, 2019, 2021 IQVIA. All rights reserved. The contents of this document are confidential and proprietary to IQVIA Holdings Inc. and its subsidiaries. Unauthorized use, disclosure or reproduction is strictly prohibited.

## 7.2 Multicenter Studies

This study will be conducted by multiple investigators at 5 Sites.

## 7.3 Missing Data

All data obtained in evaluable patients will be used in the analysis. Missing data for the primary endpoint, secondary endpoints will not be imputed.

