**Table 2 Schedule of Activities in the Event of Discontinuation**

Procedure	Study Period	Time of Intervention Discontinuation	Early Discontinuation Visit (participant withdrawn)
Full physical examination		•	•
Urine pregnancy test (WOCBP only)		•	•
Laboratory tests  (hematology and biochemistry)			•
12-lead ECG		•	•
Echocardiogram		•	•
Vital signs 		•	•
SF-36		•	•
BPI-short form		•	•
Phone contact – follow-up		• 	
Anti-AGA antibodies		•	•
Lyso-Gb3 (serum)		•	•
IARs and AE assessment		•	•
Concomitant medication review		•	•

Abbreviations: AE=adverse event; anti-AGA=anti-agalsidase; BPI=Brief Pain Inventory; COVID-19=coronavirus disease 2019; ECG=electrocardiogram; HDL=high-density lipoprotein; IARs=infusion-associated reactions; LDL=low-density lipoprotein; Lyso-Gb3=glabotriaosylsphingosine; SF-36=36-Item Short Form Survey; WOCBP=Women of childbearing potential.

1. Laboratory tests include complete hematology, blood urea nitrogen, electrolytes, phosphate, creatinine (with eGFR calculation), cholesterol (total, LDL and HDL), triglycerides, glycemia, bilirubin (total and direct), aspartate and alanine aminotransferases, alkaline phosphatase, total proteins, albumin, gamma glutamyl transferase, first morning urine and urine albumin-creatinine ratio.
2. Vital signs include heart rate, respiratory rate, body temperature, and blood pressure.
3. After intervention discontinuation, instead of following sequential procedures planned in the study, the participant should receive telephone follow-up at same timepoints of all following planned visits to evaluate general health condition.

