### **7.1 Discontinuation of Study Intervention**

It may be necessary for a participant to permanently discontinue study intervention. If study intervention is permanently discontinued, the participant will remain in the study but instead of following the sequential procedures established in the SoA, he/she will only receive telephone follow-up, if he/she agrees, at the same planned timepoints to evaluate his or her general condition. See the SoA in Section [1.3](#) for data to be collected at the time of discontinuation of study intervention and follow-up and for any further evaluations that need to be completed.

Participants will discontinue study intervention if any of the following occur:

- Eligibility criteria violation was noted after the participant started study treatment. In that case, the Sponsor, or Sponsor designee, must be contacted. An exception may be granted in rare circumstances for which there is a compelling safety reason to allow the participant to continue with study intervention. In these rare cases, the Investigator must obtain documented approval from the Sponsor, or Sponsor designee, to allow the participant to continue with study intervention.
- Participant is significantly noncompliant with study procedures which would put the participant at risk for continued participation in the study.
- Any AE, laboratory abnormality, or intercurrent illness which, in the judgment of the Investigator, presents a substantial clinical risk to the participant with continued study treatment.
- Clinically significant changes or biochemical modifications of the Lyso-Gb3 biomarker, that, at the Investigator's discretion, represent a lack of efficacy of the investigational product.

Participants who discontinue study intervention might be replaced.

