## 6.4 Retests, Unscheduled Visits and Early Termination Data

In general, for by visit summaries, data recorded at the nominal visit will be presented. Unscheduled measurements will not be included in by-visit summaries.

---

Document: \\needc-vnasc01\Biosdata\Biosidus\Agalsidase Beta\YZAA1358\Biostatistics\Documentation\SAP

Author: [name]

Version Number: V1.0

Version Date: 08May2025

Template No.: CS\_TP\_BS016 Revision 7

Reference: CS\_WI\_BS005

Effective Date: 01Nov2021

In case of retest (same visit number assigned), the latest available measurement for that visit will be used for by visit summaries but will contribute to the EOS and EOT values.

Listings will include scheduled, unscheduled, retest and early discontinuation data.

All patients who discontinued from treatment and study will be listed and the reasons for discontinuation will be tabulated.

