**The primary efficacy variable is**

#### 16.2.1 Intercurrent Event Handling and Data Imputation for Primary Efficacy Variable(s)

Not Applicable

---

Document: \\needc-vnasc01\Biosdata\Biosidus\Agalsidase Beta\YZAA1358\Biostatistics\Documentation\SAP

Author: [name]

Version Number: V1.0

Version Date: 08May2025

Template No.: CS\_TP\_BS016 Revision 7

Reference: CS\_WI\_BS005

Effective Date: 01Nov2021

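### A participant who stops before Week 26 because of a Lyso-Gb3 change judged to be lack of efficacy has no value in the ITT equivalence interval, which favours equivalence when such stops are genuine failures

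*SAP*

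**What the plan says.** Protocol 7.1 lists, among the reasons to stop study intervention, "Clinically significant changes or biochemical modifications of the Lyso-Gb3 biomarker, that, at the Investigator's discretion, represent a lack of efficacy of the investigational product". Protocol 6.8.2 leaves withdrawal from the study on the same ground to the investigator. After a permanent stop, "instead of following the sequential procedures established in the SoA, he/she will only receive telephone follow-up" (Protocol 7.1; Table 2 footnote 3 agrees). Protocol 7.1 adds: "Participants who discontinue study intervention might be replaced". Table 2 schedules a serum Lyso-Gb3 sample both when intervention is discontinued and at the early discontinuation visit.

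SAP 16.2.2 specifies a paired t-test on log Lyso-Gb3 at baseline and Week 26, with equivalence decided by the ITT 95% CI against 0.80 to 1.25. On absent values, SAP 7.3 says "Missing data for the primary endpoint, secondary endpoints will not be imputed". SAP 16.2.1, the section for intercurrent events, and SAP 6.5, the section for visit windows, are both marked Not Applicable. SAP 6.4 keeps unscheduled values out of by-visit summaries and says: "Listings will include scheduled, unscheduled, retest and early discontinuation data". The PP set (SAP 5.5) requires satisfactory completion of the study.

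**The concern.** The reason for leaving can be the endpoint itself. Week 14 is the only scheduled on-treatment Lyso-Gb3 before Week 26. A participant whose Week 14 value has risen is the one most likely to be stopped, and so most likely to have no Week 26 value. If those participants are real failures, the upper tail of the ratio distribution is trimmed before the interval is compared with 1.25. The error then favours the claim the trial is meant to test. There is no concurrent arm in which similar losses might offset it, and the PP analysis omits the same people.

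**Working it through.** **1. The plan's own figure.** Inputs from Protocol 9.4: CV 0.20, limits 0.80 to 1.25, 95% CI, power 80%, dropout 20%. Reading the CV as within-subject, the SD of the paired log difference is √2 × √ln(1 + 0.20²) = 0.280. The normal approximation gives n = ((1.960 + 1.282) × 0.280 / ln 1.25)² ≈ 16.6, so 17 against the stated 16. Then 16 / 0.8 = 20. The plan thus allows for 4 losses. With the re-estimated CV of 17.9% (SAP 16.1), the same formula gives SD 0.251.

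**2. Following one participant through the rules.** Week 14 Lyso-Gb3 is high; the investigator judges lack of efficacy and stops treatment. The discontinuation sample is drawn and telephone contact follows. There is no Week 26 sample, no window that maps the discontinuation sample to Week 26, no imputation and no intercurrent-event rule. The paired difference cannot be formed. The participant is in the ITT set but contributes nothing to its interval.

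**3. Fixed example.** Assume 20 participants, 18 centred on ratio 1.0 with log SD 0.28, and 2 stopped with Lyso-Gb3 doubled.
- Stoppers dropped: half-width 2.110 × 0.28 / √18 = 0.139, giving 1.00 (0.870 to 1.149). Equivalence is declared.
- Stoppers kept: mean log ratio 2 × 0.693 / 20 = 0.069; variance (17 × 0.28² + 18 × 0.069² + 2 × 0.624²) / 19 = 0.116, so SD 0.340; half-width 2.093 × 0.340 / √20 = 0.159, giving 1.07 (0.914 to 1.257). Equivalence is not declared.

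One such stopper does not change the decision. At log SD 0.198 it takes three: 1.00 (0.903 to 1.107) against 1.11 (0.959 to 1.284).

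**4. Simulated error rate.** Assumptions, none of them given in the documents: 20 enrolled; Week 14 and Week 26 log ratios bivariate normal with mean ln 1.25, SD 0.25 and correlation 0.5 to 0.7; a Week 14 ratio above the trigger leads to a stop with probability 50% or 100%; no replacement.

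| Analysis | Stops | False equivalence |
|---|---|---|
| All 20 with Week 26 | none lost | about 2.5% |
| Plan as written, trigger 1.4 or 1.5 | half of those above | about 5-9% |
| Plan as written, trigger 1.4 or 1.5 | all of those above | about 11-31% |
| Discontinuation value used | half or all | 1.7% or less |

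Expected stops when all above the trigger stop:
- Trigger 1.4: 20 × P(Z > ln(1.4/1.25)/0.25) = 20 × P(Z > 0.453) = 6.5.
- Trigger 1.5: 20 × P(Z > 0.729) = 4.7.
- With half stopping these become 3.3 and 2.3.

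A trigger of 2.0 with everyone above it stopping gives only 2.8-5.0% (log SD 0.198 to 0.28).

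**5. The case with no inflation.** At a true ratio of 1.0 and log SD 0.28, dropping stops triggered by noise moves the chance of declaring equivalence from about 84.5% to 76-84%. It does not rise.

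**6. Carrying the discontinuation value forward for everyone.** Suppose the true ratio is 1.25, but some participants stop for unrelated reasons after few infusions, with values still centred on 1.0 (assumed). Using those values gives false equivalence of about 5% with 2 such stoppers and 8-11% with 4, against 2.5%. A blanket rule would therefore bring back bias in the same direction.

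**The case against.** The exclusion is inferred; no sentence states it. SAP 7.3 also says that all data from evaluable patients will be used, and Protocol 7.2 says that data from replaced participants will be used. Both statements stand, but neither assigns the discontinuation value to Week 26, and evaluable is not defined. They show an intent that the SAP does not carry out.

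The route is narrow. It needs a discretionary stop between the Week 14 result and the Week 26 sample, after the investigator has separated natural history from lack of efficacy (Protocol 6.8.2). The documents do not say when central results reach the sites, and Protocol 7.2 expects withdrawal to be uncommon. All of this stands and limits how likely the problem is. It does not supply a rule for when it happens, and the fixed example needs only two such participants.

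A reader might infer that the analysis is biased toward equivalence whatever happens, or that failures vanish from the report. The documents support neither. The direction depends on the stops being genuine upward failures. SAP 6.4 lists everyone who discontinues and tabulates the reasons, so failures leave the decision interval but not the report.

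**Conclusion.** The gap is real and conditional. Following the SAP as written, a participant lost before Week 26 for a Lyso-Gb3 change has no weight in the ITT decision, and neither the PP analysis nor any stated sensitivity analysis would reveal the effect. A participant who stops after the Week 26 sample stays in the primary analysis.

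The size cannot be taken from the documents. The trigger, stop rate, correlation and SD are all assumptions. The 5-9% range is compatible with the planned dropout, at about 2 to 3 expected stops. The 11-31% range is not, because it needs about 5 to 7 stops for Lyso-Gb3 alone against 4 planned for all causes; it should be read as an upper bound and not as a forecast. The point rests on the missing rule, which should be settled before database lock because the error, if it occurs, favours the trial's claim. The text of SAP 4.2 was not available to me, and I draw nothing from it.

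**What to change.** Replace SAP 16.2.1 and, for the primary endpoint, SAP 7.3 with these rules:

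- An ITT participant who stops AGA BETA BS or is withdrawn before Week 26 for lack of efficacy or a Lyso-Gb3 change contributes the Lyso-Gb3 sample taken at discontinuation or early withdrawal (Table 2) as the post-baseline value, and stays in the analysis even if replaced.
- For stops unrelated to efficacy, such as an adverse event, pregnancy or consent withdrawal, that value is not carried forward, because it may still reflect Fabrazyme. Handle these with a mixed model on log Lyso-Gb3 using the scheduled visits already collected, plus a tipping-point analysis.
- Keep the completer paired t-test as a sensitivity analysis.
- Define evaluable, and state the fallback if no discontinuation sample was obtained, since Protocol 7.2 asks for the early discontinuation visit only where possible.

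The cost is SAP wording and additional analyses before database lock. There are no new samples, and the stopping rule is unchanged. Under the assumptions of step 4, but at a true ratio of 1.0, the loss of power against the completer analysis is about 1 to 3 points in most cases and no more than 4.

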# 8 OUTPUT PRESENTATIONS

[Appendix 1](#) shows conventions for presentation of data in outputs.

The templates provided with this SAP describe the presentations for this study and therefore the format and content of the summary tables, figures, and listings to be provided by IQVIA Biostatistics.

# 9 DISPOSITION AND WITHDRAWALS

All patients who provide informed consent will be accounted for in this study.

## 9.1 Disposition

All patients who provide informed consent and those who enter lead-in period will be accounted and presented for SCR population by treatment group and period.

The number of patients Screened, screen failed, number of enrolled, Entering Lead-in period, completing Lead-in period, discontinued during Lead-in period, Entering Treatment period, completing Treatment period, discontinued during Treatment period, reasons for Treatment discontinuation, completed or discontinued from study with the reasons for premature study discontinuation will be summarized by treatment group using incidence and percentage (n and %). The number of patients included in each analysis population will be summarized by ENR population. The confirmation of the analysis population will be finalized at a data review meeting with the Sponsor prior to final database lock. Any excluded patients will be listed and a summary of the main reason(s) for exclusion will be provided. Reason(s) for exclusion can be protocol deviations that affect the validity of efficacy outcome or treatment of the patient.

Inclusion/exclusion criteria exceptions, i.e. those patients who met exclusion criteria or who did not meet inclusion criteria but were included in the study and received treatment, will be listed by ENR Population.

---

Document: \\needc-vnasc01\Biosdata\Biosidus\Agalsidase Beta\YZAA1358\Biostatistics\Documentation\SAP

Author: [name]

Version Number: V1.0

Version Date: 08May2025

Template No.: CS\_TP\_BS016 Revision 7

Reference: CS\_WI\_BS005

Effective Date: 01Nov2021

A detailed patient wise listing will be provided for Disposition for SCR population. It will include the details for screened, completed etc with reasons for discontinuation.

## 10 PROTOCOL DEVIATIONS

Protocol deviations are the deviations from the procedure outlined in the protocol. All the Protocol Deviations (PDs) will be summarized using the ITT population as obtained from Clinical Trial Management System (CTMS) logs. PDs will be identified and discussed with the Investigator/Sponsor in PD review discussion to categorize them, and to finalize analysis population assignment.

Any PDs will be categorized into critical, major and minor protocol deviations and will be summarized based on severity categories. Critical, Major and Minor protocol deviations having impact on primary analysis will be considered while finalizing the Per Protocol (PP) Analysis population. PDs log will be used for reporting purpose in tables. PDs will be summarized based by type and severity for lead-in period and Treatment period. A by patient listing with the specific details for all protocol deviations will be provided.

## 11 DEMOGRAPHIC AND OTHER BASELINE CHARACTERISTICS

Demographic data and other baseline characteristics will be presented for the ITT population.

No statistical testing will be carried out for demographic or other baseline characteristics.

Categorical data will be summarized as frequencies, percentages and continuous data as descriptive statistics. Descriptive statistics for the following demographic and other baseline characteristics will be reported:

- Age,
- Gender
- Child Bearing potential for female patients
- Race
- Ethnicity (Hispanic or Latin origin)
- Body weight
- Height
- BMI

---

Document: \\eedc-vnasc01\Biosdata\Biosidus\Agalsidase Beta\YZAA1358\Biostatistics\Documentation\SAP

Author: [name]

Version Number: V1.0

Version Date: 08May2025

Template No.: CS\_TP\_BS016 Revision 7

Reference: CS\_WI\_BS005

Effective Date: 01Nov2021

## 12 MEDICAL AND DISEASE HISTORY

Medical history will be presented and summarized for ITT population and coded using MedDRA version 25.1 and will be recorded at the Screening visit.

Medical History conditions are defined as those conditions which stop prior to screening or at screening. All Events captured on medical history page will be included in medical history summary irrespective on end date status.

Medical history will be summarized and presented with count and percentage by SOC (System organ class) and PT (Preferred Term) wise.

Patient wise listing of medical history will be provided. Also listing for disease history will be provided separately.

## 13 MEDICATIONS

Medications will be presented and summarized using WHO DD Sept 2022 Global version.

- Prior medications are medications which started and stopped prior to first dose of study medication (AGA BETA BS) and will be presented only for Fabrazyme® for Lead-in period.
- Concomitant medications are medications which started prior to, on or after the first dose of study medication (AGA BETA BS) and ended on or after the date of first dose of study medication or were ongoing at the end of the study.

Concomitant medications will be presented only for AGA BETA BS for Treatment Period.

A combined patient wise listing for prior and concomitant medication will be provided for ITT population. Concomitant medications which will be summarized using counts and percentages by Period, treatment group.

Patients are counted only once in each therapeutic class category, and only once in each preferred term category.

Prior and concomitant medication will be summarized by Anatomical Therapeutic Chemical level 3 categories and preferred name. Prior medications will be summarized using the ITT, and concomitant medications will be summarized using the SAF.

See [appendix 1](#) for handling of partial dates for medications, in the case where it is not possible to define a medication as prior, concomitant, or post treatment, the medication will be classified by the worst case; i.e. concomitant.

---

Document: \\needc-vnasc01\Biosdata\Biosidus\Agalsidase Beta\YZAA1358\Biostatistics\Documentation\SAP

Author: [name]

Version Number: V1.0

Version Date: 08May2025

Template No.: CS\_TP\_BS016 Revision 7

Reference: CS\_WI\_BS005

Effective Date: 01Nov2021

## 14 STUDY MEDICATION EXPOSURE

Exposure to study Fabrazyme/ AGA BETA BS in weeks will be presented and summarized for the ITT population for Lead-in Period and Treatment Period respectively.

Duration of exposure (in weeks), no. of IP administrations, Number of patients exposed to IP week wise, Volume of dose administered will be summarized descriptively for Lead-in period and Treatment period.

Derivation for Duration of exposure is explained in section 14.1.

### 14.1 Derivations:(Exposure)

Duration of exposure (Weeks) = (Date of last study medication administration – Date of first study medication administration + 1)/7

If the last medication date is unknown, then the latest patients visit date will be considered for calculation of duration of exposure for the respective period. Duration of exposure will be calculated separately for Lead-in Period and Treatment period and date of study medications administration will be considered as date of administration of Fabrazyme®/AGA BETA BS depending on the study period.

Derivation for Overall compliance is explained in section 15.1

## 15 STUDY MEDICATION COMPLIANCE

Compliance to Fabrazyme/ AGA BETA BS will be presented and summarized for the ITT Population based on Lead-in Period and Treatment Period.

Non-compliance is defined as taking less than 80% of study treatment during respective evaluation period (visit to visit).

Overall compliance and class of compliance (Compliant/Non-compliant) will be presented with respect to treatment groups for respective period.

### 15.1 Derivations:(Compliance)

The formula used for calculation Overall Compliance will be as follows:

Overall Compliance (%) = (Total amount (mg) of actual doses received in each period / total amount (mg) of planned doses in each period) \* 100.

Compliance will be calculated separately for Lead-in Period and Treatment period respectively.

---

Document: \\needc-vnasc01\Biosdata\Biosidus\Agalsidase Beta\YZAA1358\Biostatistics\Documentation\SAP

Author: [name]

Version Number: V1.0

Version Date: 08May2025

Template No.: CS\_TP\_BS016 Revision 7

Reference: CS\_WI\_BS005

Effective Date: 01Nov2021

## 16 EFFICACY OUTCOMES

### 16.1 Sample Size Re-estimation (SSR)

A SSR was planned to be carried out when 50% of the total number of participants is reached. The detailed description of the SSR is defined below.

- Number of Evaluable subjects: 11 Patients were part of Intent to treat population.
- Number of subjects included for SSR: 11 Evaluable patients with Lyso GB3 data were included for SSR.
- Co-efficient of Variation estimate for Lyso-GB3: The CV (%) is estimated to be 17.9% % for 11 included patients.
- Sample size calculation based on CV estimates from the bullets above calculated using nQuery (Version 2.0.1.0): Sample size was estimated based on patient pooled variability (CV) of XX.X% (Refer to [Appendix 4 SSR Report](#))
- Assuming the true difference between AGA BETA BS and Fabrazyme is no greater than 20%, 16 Patients per group are needed to have to at least a power of 80% at type I error of 5% to obtain 95% confidence intervals for the ratio of serum level of Lyso-Gb3 marker at week 26 and serum level of the marker LysoGb3 at baseline to lie completely within the range 80% to 125% and a dropout rate of 20%.

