### **9.2.2 Primary Endpoint(s) Analysis**

The primary efficacy analysis will aim to demonstrate the equivalence in efficacy based on the mean serum Lyso-Gb3 marker ratio after 26 weeks of treatment, considering plasma level of the marker Lyso-Gb3 after 26 weeks divided by plasma level of the marker Lyso-Gb3 at baseline.

A paired t-test will be fit to the log-transformed change from baseline to after 26 weeks of treatment mean plasma Lyso-Gb3 marker.

Mean change from baseline of serum Lyso-Gb3 for after 26 weeks of treatment will be calculated and a 95% confidence interval (CI) for the difference will be computed. The mean change from baseline and its CI will be exponentiated to obtain the ratio of the means between after 26 weeks of treatment and baseline and its CI. Equivalence will be determined if the 95% CI for the postbaseline and baseline ratio lies completely within the range 0.80 to 1.25.

Analysis will be performed based on both ITT and PP populations. Descriptive statistics will be presented overall.

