## 9.4 Sample Size Determination

For the sample size calculation, the coefficient of variation of GL3 was estimated as 0.2, and the equivalence acceptance range was 20% (80% to 125%). Based on these values, the required sample size to detect equivalence with 95% confidence intervals, with a type I error of 5% and a power of 80%, was calculated as approximately 16 participants. Accounting for possible early termination, we therefore set a dropout rate of 20%, elevating the sample size to 20 participants.

The sample size of 16 is considered appropriate based on the prevalence of the disease under study and it is like previous clinical trial that evaluated a Fabrazyme® biosimilar drug.

Nevertheless, a sample size re-estimation is planned to be carried out as described in Section 9.3.1.

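### SAP 16.1 claims at least 80% power with 16 patients for true differences up to 20%, but a 20% reduction is the equivalence margin, where power is 2.5%

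*SAP*

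**What the plan says.** The decision rule is in Protocol 9.2.2: "Equivalence will be determined if the 95% CI for the postbaseline and baseline ratio lies completely within the range 0.80 to 1.25". The analysis is paired and on the log scale: "A paired t-test will be fit to the log-transformed change from baseline to after 26 weeks of treatment". SAP 16.2.2 repeats both and writes the null hypothesis so that it includes a ratio of exactly 0.80 or 1.25.

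Protocol 9.4 takes a CV of 0.2, attributed to GL3, and the 80% to 125% range. It describes "the required sample size to detect equivalence with 95% confidence intervals, with a type I error of 5% and a power of 80" percent, which "was calculated as approximately 16 participants". It then allows for attrition: "we therefore set a dropout rate of 20%, elevating the sample size to 20 participants". It gives neither the assumed true ratio nor the type of CV.

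SAP 16.1 reports the re-estimation. The CV from 11 patients is 17.9%, again without a type. The next bullet leaves its figure blank: "Sample size was estimated based on patient pooled variability (CV) of XX.X" percent. The last bullet states the result: "Assuming the true difference between AGA BETA BS and Fabrazyme is no greater than 20%, 16 Patients per group are needed" for at least 80% power at a type I error of 5%, with a 95% CI inside 80% to 125% and 20% dropout.

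**The concern.** Power for an equivalence test must be stated at an assumed true ratio inside the margins. Here the assumption offered is a difference of anything up to 20%, which on the low side is the lower margin. It appears that the width of the acceptance range has been entered as the assumed true effect.

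SAP 16.1 is the plan's account of why the size stayed at 16 evaluable patients after the re-estimation. A reader who takes it literally would believe that the trial had an 80% chance of declaring equivalence even if the products differed by 10% or 20%. That reader would then misjudge both the adequacy of the size and the meaning of a failed equivalence result.

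**Working it through.** **Inputs.** n = 16, CV 17.9%, 95% CI and limits 0.80 to 1.25 (SAP 16.1 and 16.2.2); CV 0.20 (Protocol 9.4); one group, paired t-test on logs (Protocol 9.2.2). The CV type is not given, so both readings are carried:

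- (a) within-subject CV: SD of the log ratio = √[2·ln(1+CV²)]
- (b) CV of the week-26/baseline ratio: SD of the log ratio = √[ln(1+CV²)]

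**Formula.** Equivalence is declared when the mean log ratio d and the half-width h = t(0.975, n−1)·s/√n satisfy −0.2231 + h < d < 0.2231 − h, where 0.2231 = ln 1.25. Power is the probability of this event, with d normal around the log of the true ratio and s² integrated over its chi-square distribution on n−1 degrees of freedom.

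**SAP figure reproduced.** For CV 0.179, ln(1+0.179²) = 0.03154, so the SD is 0.251 under (a) and 0.178 under (b). Under (a), at a true ratio of 1.00, the smallest n with 80% power is exactly 16, and its power is 82.6%. The SAP's 16 can therefore be obtained, but at a ratio of 1.00.

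**Power at n = 16, CV 17.9%, 95% CI**

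| True ratio | (a) within-subject | (b) CV of ratio |
|---|---|---|
| 1.00 | 82.6% | 99.4% |
| 0.95 | 70.8% | 95.1% |
| 0.90 | 41.7% | 69.9% |
| 1.20 | 8.8% | 13.6% |
| 0.80 or 1.25 | 2.5% | 2.5% |

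Power is at least 80% for true ratios of about 0.977 to 1.024 under (a) and about 0.914 to 1.094 under (b).

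**Why no sample size helps at 0.80.** The 95% CI rule amounts to two one-sided tests at 2.5% each. At a true ratio of 0.80, the test against 0.80 rejects with probability 2.5% whatever n is, and equivalence needs both tests to reject. Power at 0.80 is therefore capped at 2.5%. The same argument gives the size of the procedure: 2.5% at each margin, not the 5% quoted.

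**Sample size for 80% power, CV 17.9%.** Under (a): 16 at ratio 1.00, 20 at 0.95 and 38 at 0.90. Under (b): 9, 11 and 20.

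**Protocol 9.4, CV 0.20.** The SD is 0.280 under (a) and 0.198 under (b). At a ratio of 1.00 with a 95% CI, 16 patients give 69.2% under (a), where 19 would be needed for 80%. Under (b) they give 97.5%, and 11 would be enough. Under (b), 16 is exactly the number required at a true ratio of 0.93. The dropout step is correct: 16/0.8 = 20.

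**The case against.** The strongest defence is that the sentence is a slip of wording. Protocol 9.4 calls the acceptance range 20%, so the SAP's author probably meant the margin, not the true difference. The SAP's 16 does reproduce at a CV of 17.9%, a 95% CI and a ratio of 1.00. The margin, test and decision rule are unaffected. The bullet with the blank CV points back to the CV reported above it, where 17.9% is the only figure, and to the Appendix 4 report. That report is an embedded file whose content is not in the text, so the CV type, true ratio and software settings may be recorded there. A type I error of 5% beside a 95% CI follows the two-sided convention in SAP 6.6, and a true size of 2.5% is conservative. Appendix 1 of the SAP uses treatment-group labels for the two study periods, so 'per group' is loose but not unintelligible.

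Most of this stands. The size of 16 is not shown to be wrong, and the blank CV, 'per group' and the 5% label are secondary clean-ups. The defence does not rescue the power sentence. If the author meant the margin, the text still says the true difference, and under neither CV definition is the statement correct as written.

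**Conclusion.** The power claim in SAP 16.1 is wrong as written and should be corrected. With 16 patients and a CV of 17.9%, power at a true 10% reduction is 42% to 70%. At a true 20% increase it is 9% to 14%, and at a true 20% reduction it is 2.5%. The 80% applies only close to a ratio of 1.00, within the ranges given above.

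These figures assume log-normal data and take 17.9% as the true CV, although it was estimated from only 11 patients.

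A reader might infer three stronger things that the documents do not support:

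- **That the SAP's 16 works only at a ratio of exactly 1.00.** It keeps 80% power over a band around 1.00, narrow under reading (a) and wider under (b).
- **That the protocol's 16 is too small.** This is so only if 0.20 is a within-subject CV. If it is the CV of the ratio, power is 97.5% at a ratio of 1.00.
- **That the protocol's 16 was calculated for a 90% CI.** Under (a), a 90% CI needs 15 patients, and 16 give 83.7%. Other routes come as close: a normal approximation with a 95% CI gives 17, and the plain two-sample formula with difference 0.2 and SD 0.2 gives 2 × (1.96 + 0.84)² ≈ 15.7, hence 16 per group. Since Protocol 9.4 states neither the CV type nor the true ratio, the origin of its 16 cannot be settled.

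**What to change.** **SAP 16.1**

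- Delete the clause about a true difference of no more than 20%, and the words 'per group'.
- State a single group with 16 evaluable patients, and the true ratio assumed.
- Replace the XX.X placeholder with the CV used, and say whether it is within-subject or the CV of the week-26/baseline ratio.
- Give power at true ratios 1.00, 0.95 and 0.90 (83%, 71% and 42%, or 99%, 95% and 70%, according to the CV type).
- Note that the 95% CI rule has a one-sided size of 2.5% at each margin.

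**Protocol 9.4**

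- State the type of the 0.20 CV and the true ratio behind the 16.
- Only if it is a within-subject CV at a ratio of 1.00, restate the power as about 69% and say that 19 evaluable patients would be needed for 80%.
- If it is the CV of the ratio, say that 16 give 97.5% at a ratio of 1.00.

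**Cost.** Wording in two sections. No patients are added, and no test, margin or decision rule changes. The price is a stated power that looks less favourable away from a ratio of 1.00.
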